## 9.2 Setting

### 9.2.1 Target Population

Patients are eligible for observation in this study, if the following applies:

**Inclusion Criteria:**

- Male and female patients aged  $\geq 18$  years
  - Treatment-naïve patients
  - Patients monoinfected with CHCV, GT1 (confirmed within the last 36 months or at physicians discretion in case of risk factors)
  - Non-cirrhotic patients (based on liver biopsy, fibroscan  $\leq 9.6$ kPa and/or clinical signs)
  - The decision to treat with 3D regimen is made by the physician in accordance with the local Swiss product label prior to any decision to approach the patient to participate in this study.
  - Patients with debilitating fatigue (FSS  $\geq 4$ )
-

- Patients willing to participate in the study, and willing to wear an activity tracker

**Exclusion Criteria:**

- Patients with sources of fatigue other than HCV (especially, severe depression (Annex 4), cancer and hormonal disorders causing clinically significant fatigue)
- Patients with conditions that do not allow to adhere to protocol and use of the device at investigator's discretion
- Patients being wheelchair dependent

**9.2.2 Study Duration**

This is a prospective, observational study. The enrollment period will be approximately 12 months and the duration of the observational period will be approximately 28 weeks for each patient. Patients may discontinue treatment or the study at any time without prejudice.

**9.2.3 Investigator Selection Criteria**

The sites will be selected based on the availability of patient population targeted for this study. The selected investigators (qualified by training and experience) and study sites (with proven experience and competence in treating HCV patients) will have the ability to appropriately conduct this observational study in accordance with applicable legal and regulatory requirements.

**9.3 Variables**

**9.3.1 Primary Variable**

- Change of mean daytime physical activity between baseline (before treatment start) and post-treatment week 12

### **9.3.2 Secondary Variables**

- Change of Fatigue Severity Score (FSS) between baseline, during and after 12 weeks of treatment with 3D regimen
- Correlation between mean daytime physical activity and FSS at baseline, during and after 12 weeks of treatment with 3D regimen
- Proportion of patients achieving SVR12 after treatment with 3D regimen (defined as HCV RNA not detectable 12 weeks after the last actual dose of 3D regimen)
- Sleep efficiency at baseline, during and after 12 weeks of treatment with 3D regimen

### **9.4 Data Sources**

Source documents are defined as original documents. The investigator will document patient data, including FSS, in his/her own patient files which will serve as source data for the study. Physical activity and sleep data will be collected by use of wrist-worn activity trackers (ActiGraph GT9X Link) which will be processed by device-specific software to obtain the physical activity and sleep-related variables for analysis.

All data collected by the activity tracker will be analyzed by the biostatistician at the end of the study. The data will not be seen by the investigators and patients at any time during data collection (between visit 1 and visit 5 (Figure 1: Study Activities)).

### **9.5 Study Size**

Observational research is exploratory in nature and there are no pre-specified hypotheses to be tested. Hence, there is no need for power calculation. The primary endpoint in this study is derived from an activity tracking device.

In the literature, no data on actigraphy in HCV patients suffering from fatigue are available that would allow statistical sample size calculation focusing on the precision of estimation of the primary endpoint.

On the other hand, the patient selection criteria only allow recruitment of a restricted number of patients in a justifiable period of time. We assume that a total of 100 patients are sufficient to provide stable results regarding investigation of the study objectives.

The planned study size of 100 will have 80% power to detect a change from baseline of the effect size 0.29 using a two-sided one-sample t-test with a significance level of 5%.

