**Study Size:**

Approximately 100 patients in Switzerland will be enrolled.

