If the investigator sees the medical indication to initiate treatment with 3D regimen before the patient has worn the activity tracker for at least 4 weeks during the treatment preparation phase, or if 3D regimen is discontinued at the investigator's discretion, the patient will discontinue study participation. ActiGraph GT9X Link comes with a wear time sensor that automatically detects if a wrist worn device has been removed. Thus, patient compliance to the tracker will be measured by this wear time sensor. If values are missing for a total of  $\geq 2$  hours during daytime, this day will be declared as non-eligible. In order to complete the data set of 2 weeks (10 working days) any non-eligible day will be replaced by daytime values in a pre-defined order, starting with the most recent day of the respective foregoing week (Figure 1). Weekend days are excluded from analysis.

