#### Questionnaire

Patients will be asked to complete the Fatigue Severity Scale (FSS) before treatment start and at each visit as part of routine practice. The FSS is a nine-item questionnaire assessing the functional impact of fatigue during the past two weeks on multiple life domains using scales from 1 (strongly disagree) to 7 (strongly agree). The fatigue score is the mean score of the 9 items. Clinically significant fatigue is usually defined as score equal or above "4" [\[38, 39\]](#). The routinely assessed FSS score to be used within this study should not include questionnaire results older than 3 months before visit 1. Patients with an average FSS score < 4 at visit 2 will discontinue study participation.

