### 9.1.4 Termination Criteria

A patient may withdraw from the study at any time. The investigator may discontinue any patient's participation for any reason. AbbVie AG may interrupt/stop the study at any time for any reason.

If a patient withdraws or is lost to follow-up, the reason for withdrawal will be recorded in the CRF if voluntarily shared by the patient. In case of study termination, the investigator must ensure that the patient returns the activity tracker, and that no subsequent activity tracker will be shipped to the patient.

Specifically, the following termination criteria apply:

- Patients not eligible for treatment with 3D regimen in accordance with the Swiss product label and according to the investigator's judgment will discontinue study participation.
- Patients who discontinue treatment with 3D regimen or who do not wear the activity tracker for at least 3 weeks before each visit will be withdrawn from the study. In case the decision to discontinue treatment with 3D regimen was taken before or during a routine clinic visit, this visit will be considered the last study visit. The last dose of treatment of 3D regimen will be recorded in the CRF.
- Patients with an average FSS score < 4 at visit 2 will discontinue the study.

Following discontinuation of the study, the patient will be treated in accordance with the investigator's best clinical judgment.

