3.1 Handling of Missing Data

- Missing data from CRFs will be proven within the data collection in OpenClinica and clarified by queries to the monitoring.
- For tracker variables datasets of two eligible weeks (10 working days) are needed. If less than two eligible weeks are available, daytimes variables of previous weeks will be used.
- No other replacement of missing data will take place.

4 Objectives

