5.2 Analysis Populations (ITT and mITT)

The statistical analyses will be performed for the intention-to-treat population (ITT) and the modified ITT population (mITT) as well. The ITT consists of all documented patients of the overall population with treatment as intended to protocol and received study medication at least once. Additionally, mITT consists of all patients of the ITT which take part at all five visits. For ITT and mITT descriptive and safety parameters will be analyzed. Primary and secondary endpoints will be analyzed for mITT.

6 Statistical Methods

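### The 80% power at effect size 0.29 is stated for the 100 patients enrolled, but the primary test uses only five-visit completers with usable tracker data; the figure holds only if at least 96 are evaluable

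*Protocol*

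**What the plan says.** Protocol 9.5 describes the study as exploratory, with no hypotheses fixed in advance and no need for a power calculation. It then gives one: "The planned study size of 100 will have 80% power to detect a change from baseline of the effect size 0.29", for a two-sided one-sample t-test at the 5% level. Protocol 9.7 specifies that test for the primary variable. SAP 6.3.1 keeps the two-sided 5% level but allows a t-test or a Wilcoxon test, depending on the distribution.

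The number 100 is an enrolment figure. The abstract says: "Approximately 100 patients in Switzerland will be enrolled".

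The analysis set is smaller. SAP 5.2 says "Primary and secondary endpoints will be analyzed for mITT", and defines it thus: "mITT consists of all patients of the ITT which take part at all five visits".

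The protocol lists several ways to leave before that point:
- Section 9.1.1 discontinues patients whose treatment starts "before the patient has worn the activity tracker for at least 4 weeks during the treatment preparation phase".
- The Questionnaire paragraph of 9.1.1, repeated in 9.1.4, says: "Patients with an average FSS score < 4 at visit 2 will discontinue study participation".
- Section 9.1.4 withdraws patients who stop the 3D regimen, and says that those "who do not wear the activity tracker for at least 3 weeks before each visit will be withdrawn from the study".

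SAP 3.1 lets tracker days from earlier weeks complete the required ten working days. Beyond that, "No other replacement of missing data will take place".

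**The concern.** The power is computed for one group and the test is run in another. Each route out of the study, and each missed visit, reduces the number tested. The mITT is defined by attendance rather than tracker wear, so a patient can belong to it and still have no usable value at baseline or visit 5. With no imputation for that patient, the number tested can fall below the mITT as well. Neither document gives a dropout rate, an inflated enrolment or a target number of evaluable patients.

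A reader of 9.5 will take 80% at 0.29 as the sensitivity of the primary analysis. If the analysed number is well below 100, a non-significant result would be read against a sensitivity that the study did not have.

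**Working it through.** **Inputs.** From Protocol 9.5: N = 100, effect size d = 0.29 (mean change divided by the SD of the change), two-sided α = 0.05, one-sample t-test, stated power 80%. From the abstract: 100 is the number enrolled. From SAP 5.2: the test is run in patients with all five visits. Attrition rate: not given in either document.

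**Formula.** With n evaluable patients, the test statistic follows a noncentral t distribution with n − 1 degrees of freedom and noncentrality d√n. Power = P(T > t₀.₉₇₅,ₙ₋₁) + P(T < −t₀.₉₇₅,ₙ₋₁).

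**The plan's own figure.** For n = 100, the noncentrality is 0.29 × √100 = 2.90 and the critical value is 1.984. Power is 81.9% (82.6% by the normal approximation). The stated 80% is therefore reproduced, with a small margin. The effect detectable with exactly 80% power at n = 100 is 0.283.

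**Smallest n that keeps 80%.** At n = 96, the noncentrality is 0.29 × √96 = 2.841 and power is 80.3%. At n = 95 it is 2.827 and power is 79.9%. The threshold is 96, so at most 100 − 96 = 4 patients may be lost. The normal approximation puts the threshold at 94.

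**Power and precision by number evaluable.** The 95% confidence-interval half-width of the mean change, in SD units, is t₀.₉₇₅,ₙ₋₁/√n; for n = 80 this is 1.990/8.944 = 0.223.

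| Evaluable n | Loss from 100 | Power at 0.29 | Effect detectable with 80% power | 95% CI half-width (SD units) |
|---|---|---|---|---|
| 100 | 0% | 81.9% | 0.283 | 0.198 |
| 96 | 4% | 80.3% | 0.289 | 0.203 |
| 95 | 5% | 79.9% | 0.290 | 0.204 |
| 90 | 10% (assumed) | 77.7% | 0.299 | 0.209 |
| 80 | 20% (assumed) | 72.7% | 0.317 | 0.223 |
| 70 | 30% (assumed) | 66.7% | 0.340 | 0.238 |

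The reasons for leaving overlap and have no stated rates, so they cannot be added up. The 10% to 30% rows show a range and are not a forecast.

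**Wilcoxon option.** All figures above are for the t-test. If the SAP's Wilcoxon test were used on near-normal data, with an assumed relative efficiency of 0.955, 100 patients would count as about 95 (100 × 0.955 = 95.5, rounded down). Power would be 79.9%, leaving almost no room for loss.

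**The case against.** The best defence is that nothing in 9.5 is miscalculated and little depends on it. The section calls the study exploratory, sets N by feasible recruitment and ties 0.29 to no clinical threshold. At N = 100, 0.29 is simply the smallest two-decimal effect with at least 80% power (0.28 gives 79.2%). Ten per cent loss moves that effect to 0.30, which changes no decision. The line at 96 is also sharper than it deserves: 95 gives 79.9%, 91 still gives 78.1%, and enrolment is only approximately 100. The report will show valid and missing N, confidence intervals and a flowchart, so readers will see the precision achieved. The protocol also acts to limit loss, through reminder calls, staff training, a patient brochure and checks of tracker handling at visits 2 to 5. Finally, investigators do not see tracker data during collection, so it is unclear how the low-wear withdrawal rule would operate before visit 5.

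Much of this stands. It is not an arithmetic error, the loss of a few patients is immaterial, and larger shortfalls rest on assumed rates. The low-wear rule may also remove fewer patients in practice than its wording suggests.

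It does not remove the mismatch. Having stated a power for a 5% test, the protocol should state it for the group tested. Reporting the achieved N afterwards does not correct the planning figure. Measures against loss are not an allowance for it, and an unknown rate is itself a reason to give power by number evaluable.

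**Conclusion.** The concern holds. The 80% at 0.29 is correct for 100 analysed patients, but the plan secures it only if no more than 4 of the 100 enrolled lack an evaluable primary endpoint. Under assumed losses of 10%, 20% and 30%, power falls short of 80% by 2.3, 7.3 and 13.3 percentage points. The threshold of 96 rests on the exact t-test, an effect size of exactly 0.29 and enrolment of exactly 100.

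The effect is modest. The design, the population and the conduct of the test are untouched; what is overstated is the sensitivity claimed for the primary analysis. It should be corrected, but it does not put the study in question.

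**What to change.** Restate the last paragraph of Protocol 9.5 by number evaluable. The protocol does not define the mITT, so either describe the group in words, as below, or refer to SAP 5.2. Suggested text:

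> Approximately 100 patients will be enrolled. For the two-sided one-sample t-test at the 5% level, 80% power at an effect size of 0.29 requires at least 96 patients who attend all five visits and have evaluable tracker data at baseline and visit 5. The loss rate is not known. If 90, 80 or 70 patients were evaluable (illustrative assumptions), power at 0.29 would be 78%, 73% or 67%; the effect size detectable with 80% power would be 0.30, 0.32 or 0.34; and the half-width of the 95% confidence interval for the mean change would be 0.21, 0.22 or 0.24 SD.

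The half-widths give a precision statement without the literature data that 9.5 says are lacking, although only in SD units. A sentence noting that these figures are for the t-test would cover the Wilcoxon option in SAP 6.3.1.

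The cost is one paragraph and a slightly less favourable stated figure. No extra patients, visits or analyses are needed.

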## **9.6 Data Management**

Data for this study will be recorded in English by each participating center on case report forms (CRFs). Examinations, diagnostic measures, laboratory assessments, findings and observations routinely performed in this cohort, will be transcribed by the investigator or designee from the source documents into the CRF. Only data specified in the observational plan will be entered into the CRF. For each enrolled patient, the investigator or designee will create a new patient file in the CRF.

The investigator or designee will deliver the activity tracker to the study designated biostatistician following the last scheduled patient visit (Table 1). Activity tracker collected data will then be transferred to the data processing software ActiLife 6 [\[27\]](#).

Besides the tracker data, CRF data will be evaluated by a study designated biostatistician.

## **9.7 Data Analysis**

All data will be analyzed by descriptive statistical methods.

Quantitative data (e.g. the primary variable) will be analyzed by the statistical parameters valid N, missing N, mean, standard deviation (SD), and selected quantiles: minimum (0%), lower quartile (25%), median (50%), upper quartile (75%), and maximum (100%). If indicated by the data, an additional frequency distribution will be supplied after appropriate grouping of data.

Qualitative (e.g. achievement of SVR12 (yes/no)) and categorical variables (e.g. individual items of the FSS) will be presented by (absolute and relative) frequency distributions.

The primary variable will be tested using the one-sample t-test (two-sided) on the 5% significance level.

Two-sided 95% confidence intervals will be provided for mean daytime physical activity, FSS and sleep efficiency by visit and for the changes between start of treatment and the respective follow-up visits. A 95% confidence interval for the proportion of patients achieving SVR12 will also be calculated.

The correlation between the physical activity (assessed by the activity tracker) and the fatigue score (assessed by FSS) will be investigated by visit and for the changes between baseline and follow-up visits, using Spearman's rank correlation coefficient.

Subgroup analyses will be provided for patients who achieve / do not achieve SVR12 after treatment with 3D regimen.

All statistical analyses will be carried out by means of the SAS® package (version 9.2 or higher).

Details of planned analyses will be described in a separate statistical analysis plan (SAP).

## **9.8 Quality Control**

The sites will be instructed in the observational plan, the handling of the CRF and activity tracker, and the requirement to maintain source documents for each patient in the study (see Section 9.4).

Follow-up on CRF data for medical plausibility will be done by AbbVie personnel (or their representatives). The investigator of each site will finally review the CRFs for completeness and accuracy of available data and provide his or her signature and date to CRFs as evidence thereof.

Continuous monitoring of the study and frequent site telephone contacts will be done by AbbVie or a Contract Research Organization (CRO) working on behalf of AbbVie.

Patients will not be compensated for their participation in this PMOS study. Participating physicians will be offered compensation by AbbVie for compiling and submitting clinical information for use in this PMOS study according to the regulatory requirements in Switzerland. In case of inconsistent data entry, the physician will be contacted during query management to complete data of concerned visits. Without complete documentation only partial payment of visits will be performed. Amount of payment per Visit will be documented in contracts between participating site and AbbVie.

## **9.9 Limitations of the Research Methods**

The limitations of observational studies, such as uncontrolled confounding by lack of randomization, and difficulties to clearly interpret treatment effects in the context of missing data are well known. Their validity can be increased by accurate outcome measurements, documentation of the most common confounders, sufficient length of follow-up and by activities to obtain complete recording of available data as well as by searches for missing key data.

The most important outcome measure in this study is the measurement of physical activity by the ActiGraph GT9X Link. Failure in wearing the device or misuse may lead to erroneous estimation of the real physical activity pattern of the respective patient.

## **9.10 Other Aspects**

N/A

## **10.0 Protection of Human Subjects**

This observational study will be run in compliance with local laws and regulations.

Notification/submission to the responsible regulatory authorities, Ethics Committee (EC) and/or Competent Authorities (CAs) will be done as required by local laws and regulations.

The investigator is responsible to ensure that written informed consent to use and/or disclose patients' anonymized health data will be obtained prior to patient inclusion.

To maintain patient confidentiality, no demographic data that can identify the patient will be collected (e.g. initials, date of birth) - only the patient age will be collected. In order to protect patient identity, a unique number will be assigned to each patient and related study records.

The study will be entirely financed by AbbVie AG. The patient will not be paid for his participation in the study.

## **11.0 Management and Reporting of Complaints**

A Complaint is any written, electronic, or oral communication that alleges deficiencies related to the physical characteristics, identity, quality, purity, potency, durability, reliability, safety, effectiveness, or performance of a product/device after it is released for distribution.

Complaints associated with any component of this product/device must be reported to the Sponsor (Section 11.2.2). For adverse events, please refer to Sections 11.1.1 through 11.1.7. For product complaints, please refer to Section 11.2.

## 11.1 Medical Complaints

### 11.1.1 Adverse Event Definition and Serious Adverse Event Categories

An adverse event (AE) is defined as any untoward medical occurrence in a patient, which does not necessarily have a causal relationship with their treatment. An AE can therefore be any unfavorable and unintended sign (including an abnormal laboratory finding), symptom, or disease temporally associated with the use of a medicinal product, whether or not the event is considered causally related to the use of the product.

Such an event can result from use of the drug as stipulated in the labeling, as well as from accidental or intentional overdose, drug abuse, or drug withdrawal. Any worsening of a pre-existing condition or illness is considered an AE. An AE can also derive from the medical device ActiGraph GT9X Link, which is used in this study. Minimal risks related to the Activity Tracker can be possible discomfort wearing the device around the clock and possible skin rash or skin irritation caused by the device.

Patient reported FSS questionnaire data are not considered a potential source of adverse reactions. However, participating sites should review the questionnaire data and if a possible product-related event (including a suspected adverse reaction) is noted, the Health Care Professional must determine whether the event is related to an AbbVie authorized product and if so, it should be reported to AbbVie. If an increase in the FSS score by  $\geq 1$  point is observed, the investigator must report this increased fatigue as an AE to AbbVie.

Patient derived activity tracker data are not considered a potential source of adverse reactions. Physicians are not able to see tracker data at any time. Thus, if a possible product-related event (including a suspected adverse reaction) is noted, activity tracker derived mean values of interest will be reported exclusively at the end of the study by the bio-statistician to the AbbVie PV team.

If an AE meets any of the following criteria, it is considered a serious adverse event (SAE):

---

Death of Patient:	An event that results in the death of a patient.
Life-Threatening:	An event that, in the opinion of the investigator, would have resulted in immediate fatality if medical intervention had not been taken. This does not include an event that would have been fatal if it had occurred in a more severe form.
Hospitalization:	An event that results in an admission to the hospital for any length of time. This does not include an emergency room visit or admission to an outpatient facility.
Prolongation of Hospitalization:	An event that occurs while the study patient is hospitalized and prolongs the patient's hospital stay.
Congenital Anomaly:	An anomaly detected at or after birth or any anomaly that results in fetal loss.
Persistent or Significant Disability/Incapacity:	An event that results in a condition that substantially interferes with the activities of daily living of a study patient. Disability is not intended to include experiences of relatively minor medical significance such as headache, nausea, vomiting, diarrhea, influenza, and accidental trauma (e.g., sprained ankle).
Important Medical Event Requiring Medical or Surgical Intervention to Prevent Serious Outcome:	An important medical event that may not be immediately life-threatening or result in death or hospitalization, but based on medical judgment may jeopardize the patient and may require medical or surgical intervention to prevent any of the outcomes listed above (i.e., death of patient, life threatening, hospitalization, prolongation of hospitalization, congenital anomaly, or persistent or significant disability/incapacity). Additionally, any elective or

spontaneous abortion or stillbirth is considered an important medical event. Examples of such events include allergic bronchospasm requiring intensive treatment in an emergency room or at home, blood dyscrasias or convulsions that do not result in inpatient hospitalization, or the development of drug dependency or drug abuse.

